- b. The efficacy of contraception by hormone preparations may decrease as a result of the interaction with the investigational product. In that case, the subject should use two extremely effective methods of contraception during the treatment period and at least for 3 months after the last dose of the investigational product.

Pregnancy test

- A woman of childbearing potential can be enrolled to this study only if it is confirmed that she is negative in a highly sensitive serum pregnancy test along with her menstrual period.
- Pregnancy test should be performed if no menstruation occurred or she is suspected to be pregnant.
- Analysis should be performed according to the package insert using a testing kit provided by GSK.

Collection of pregnancy information**If a male study subject's partner becomes pregnant**

- Investigator will attempt to collect pregnancy information on any male participant's female partner of a male study participant who becomes pregnant while participating in this study. This applies only to participants who receive study treatment.
- After obtaining the necessary signed informed consent from the pregnant female partner directly, the investigator will record pregnancy information on the appropriate form and submit it to GSK within 2 weeks of learning of the partner's pregnancy.
- Partner will also be followed to determine the outcome of the pregnancy. Information on the status of the mother and child will be forwarded to GSK
- Generally, follow-up will be no longer than 6 to 8 weeks following the estimated delivery date. Any termination of the pregnancy will be reported regardless of fetal status (presence or absence of anomalies) or indication for procedure.

Female Participants who become pregnant

- Investigator will collect pregnancy information on any female participant, who becomes pregnant while participating in this study.
- Information will be recorded on the appropriate form and submitted to GSK within 24 hours of learning of a participant's pregnancy.
- Participant will be followed to determine the outcome of the pregnancy. The investigator will collect follow up information on participant and neonate, which will be forwarded to GSK Generally, follow-up will not be required for longer than 6 to 8 weeks beyond the estimated delivery date.
- Any termination of pregnancy will be reported, regardless of fetal status (presence or absence of anomalies) or indication for procedure.

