- ii) Women of childbearing potential who content to follow the guidance about contraception on attachment 5 during the study period and at least for 3 months after the last dose of the product.
- iii) No plan of pregnancy during the study period

Informed Consent

11. Patients who have ability to sign their name on the ICF, following the description on attachment 3, adhering to the requirements and limitations described on the ICF and the protocol.

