6.1. Inclusion Criteria

6.1.1. Screening Phase (Day -28 to Day -1)

In the screening phase, subjects eligible for enrolment in the study must meet all of the following criteria. Laboratory parameters should be measured by 7 days (± 3 days) before initial injection (Day 1).

Age

1. Between 20 and 80 years of age at the time of informed consent (ICF).

Subjects and Characteristics of the Disease

2. Patients with at least a 3-month history of upper limb spasticity after the most recent stroke
3. Patients who have spastic symptoms in the finger (including the thumb), wrist, and elbow flexors whom the investigator considers the injections of 400 units of the product is necessary for the upper limb based on the muscle spasms and the symptoms of the patient
4. Patients who have a previous treatment history of 240 units of the product for the upper limb at least 16 weeks before screening (refer to [Table 3](#) for muscles in the upper limbs)
5. Patients who meet following criteria on MAS at screening (Test position: sitting)
 - At least 3 in for the elbow flexors
And
 - At least 2 in the finger or wrist flexors
6. Patients who have severe upper limb spasticity, which deserves to be treated with 400 units of the product in the divided dose and was previously injected 240 units of the product
7. Patients whom the investigator considers that enrolment in the study poses no problems based on the laboratory data results at screening
8. Patients who are free from a history of acute decreased lung function (hospitalization with aggravated asthma/COPD, pneumonia, or signs of pneumonia, or abnormal reactive airway diseases suggested on X-rays) within the last 3 months at screening and have stable pulmonary function (SpO_2 value is $\geq 95\%$)

Body Weight

9. Body weight ≥ 40 kg at screening

Sex

10. Male or female

a. Male Subjects

Male subjects must content to use highly effective contraceptive methods, which are shown on attachment 5 of the protocol in detail during the study period, and sperm donation must be avoided.

b. Female Subjects

Female subjects who are not pregnant or lactating are considered eligible (refer to attachment 5) if at least one of the following criteria is met:

- i) Non-childbearing potential based on the definition on attachment 5

- ii) Women of childbearing potential who content to follow the guidance about contraception on attachment 5 during the study period and at least for 3 months after the last dose of the product.

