9.2.6. Pregnancy

- Details of all pregnancies in female partners of male participants will be collected after the start of study treatment and until Final Visit.
- If a pregnancy is reported, the investigator should inform GSK within 24 hours of learning of the pregnancy and should follow the procedures outlined in Appendix [X].
- Abnormal pregnancy outcomes (eg, spontaneous abortion, fetal death, stillbirth, congenital anomalies, ectopic pregnancy) are considered SAE.

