- b. The efficacy of contraception by hormone preparations may decrease as a result of the interaction with the investigational product. In that case, the subject should use two extremely effective methods of contraception during the treatment period and at least for 3 months after the last dose of the investigational product.

Pregnancy test

- A woman of childbearing potential can be enrolled to this study only if it is confirmed that she is negative in a highly sensitive serum pregnancy test along with her menstrual period.
- Pregnancy test should be performed if no menstruation occurred or she is suspected to be pregnant.
- Analysis should be performed according to the package insert using a testing kit provided by GSK.

Collection of pregnancy information**If a male study subject's partner becomes pregnant**

- Investigator will attempt to collect pregnancy information on any male participant's female partner of a male study participant who becomes pregnant while participating in this study. This applies only to participants who receive study treatment.
- After obtaining the necessary signed informed consent from the pregnant female partner directly, the investigator will record pregnancy information on the appropriate form and submit it to GSK within 2 weeks of learning of the partner's pregnancy.
- Partner will also be followed to determine the outcome of the pregnancy. Information on the status of the mother and child will be forwarded to GSK
- Generally, follow-up will be no longer than 6 to 8 weeks following the estimated delivery date. Any termination of the pregnancy will be reported regardless of fetal status (presence or absence of anomalies) or indication for procedure.

Female Participants who become pregnant

- Investigator will collect pregnancy information on any female participant, who becomes pregnant while participating in this study.
- Information will be recorded on the appropriate form and submitted to GSK within 24 hours of learning of a participant's pregnancy.
- Participant will be followed to determine the outcome of the pregnancy. The investigator will collect follow up information on participant and neonate, which will be forwarded to GSK Generally, follow-up will not be required for longer than 6 to 8 weeks beyond the estimated delivery date.
- Any termination of pregnancy will be reported, regardless of fetal status (presence or absence of anomalies) or indication for procedure.

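### Pregnancy collection for female subjects ends with participation, while their contraception period runs at least 3 months past the last dose; women withdrawn soon after an injection fall in the gap

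*Protocol*

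**What the plan says.** All references are to the current protocol text (Amendment 2).

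- **Contraception, women.** Section 6.1.1, criterion 10b ii, binds women of childbearing potential "during the study period and at least for 3 months after the last dose of the product". Note b to Table 11 in Appendix 5, on hormonal methods whose effect may be reduced, uses the same length: "during the treatment period and at least for 3 months after the last dose of the investigational product".
- **Contraception, men.** Section 6.1.1, criterion 10a, binds male subjects "in detail during the study period, and sperm donation must be avoided". Appendix 5 adds no post-dose period for them.
- **Collection, female subjects.** Appendix 5: "Investigator will collect pregnancy information on any female participant, who becomes pregnant while participating in this study". The form goes to the sponsor within 24 hours of learning of the pregnancy.
- **Collection, partners.** Section 9.2.6: "Details of all pregnancies in female partners of male participants will be collected after the start of study treatment and until Final Visit".
- **Timing, partners.** Section 9.2.6 says that if a pregnancy is reported, "the investigator should inform GSK within 24 hours of learning of the pregnancy". Appendix 5 tells the investigator, after obtaining the partner's consent, to record the information on a form and "submit it to GSK within 2 weeks of learning of the partner's pregnancy".
- **After the study.** Appendix 5 makes a related SAE of a post-study pregnancy reportable, without a duty to look for it. Section 9.2.1 has the same passive rule for any related SAE in a former participant.
- **Leaving early.** Section 8.1 treats stopping treatment as withdrawal from the study. Section 8.2 requires the termination visit promptly after the decision.

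Section 9.2.6 sends the reader to an appendix whose number was never filled in; it still reads [X].

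**The concern.** The end of the contraception obligation is measured from the last dose. The end of pregnancy collection is measured from participation. Nothing in the protocol makes the two coincide, and no passage bridges them.

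A woman who stops early is the case that matters. She remains under the contraception requirement for at least 3 months after her injection, but leaves the collection rule as soon as her termination visit is done. If she then conceives inside that period, the pregnancy is neither recorded nor followed to outcome. It reaches the sponsor only if it produces an SAE judged related and the investigator hears of it. An uncomplicated pregnancy, or one with an outcome judged unrelated, would not appear at all. The safety record at 400 units would then be thinnest in women who were withdrawn, including those withdrawn for QTc, a treatment-related SAE or a prohibited therapy (8.2.2, 8.2.3, 8.2.5).

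A second, smaller matter is the wording of 9.2.6. Its only collection rule concerns partners, its cross-reference is blank, and its 24-hour instruction stands beside a 2-week rule for partner pregnancies in Appendix 5 with no statement of how the two fit together.

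**Working it through.** The protocol states no figure for this gap, so there is none to reproduce. The check is day counting.

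**Inputs**

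- Contraception period after the last dose: at least 3 months (6.1.1). Taken as 89 to 92 days; 91 days = 13 weeks where one value is needed.
- Latest possible injection: Week 36, day 36 × 7 = 252 (5.1.3.1).
- Final Visit for completers: Week 48, day 48 × 7 = 336, window ±4 days (Schedule of Activities).
- V5 in the open-label parts: 12 weeks after that part's injection, window ±4 days (current Schedule of Activities). For a subject injected at Weeks 0, 12, 24 and 36, the Week 48 visit is also the completion visit (Figure 1 text).
- Qualification visit window: ±14 days in the current Schedule of Activities. The footnote text printed with the pre-amendment schedule keeps −14 days at Week 36 and limits the late side to +4.
- Termination visit after withdrawal: prompt, so possible at any time after a dose (8.2).

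**Formula.** Days uncovered = max(0, 3 months − days from last dose to last visit).

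**Early withdrawal.** Termination visit 14 days after an injection: 91 − 14 = 77 days, which is 77 / 7 = 11 of 13 weeks. The earlier the withdrawal after a dose, the nearer this comes to the whole 3 months.

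**Completers**

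| Last dose | Last visit | Days between | Uncovered, against 89 to 92 days |
|---|---|---|---|
| Week 36, nominal (day 252) | Week 48 (day 336) | 84 | 5 to 8 |
| Week 36, V5/Final Visit at its earliest | 84 − 4 days after dose | 80 | 9 to 12 |
| Week 36 visit held 14 days early (day 238) | Week 48 + 4 (day 340) | 102 | none |
| Week 28 (day 196) | Week 48 (day 336) | 140 | none |
| Week 24 (day 168) | Week 48 (day 336) | 168 | none |

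**Number at risk.** Section 10.1 expects about 100 of about 120 subjects to complete, so 120 − 100 = about 20 would not. The protocol does not say how many of these would be women of childbearing potential, or when after a dose they would leave. No expected count of missed pregnancies can be derived.

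**When participation ends.** Section 5.3 defines completion as having finished all procedures including the completion visit, and 9.2.1 speaks of former participants once a subject has been discharged. Read together, they leave no room for treating a woman as still participating after her termination visit.

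**The case against.** The protocol is not silent after the study. Related SAEs learned of later must be notified (9.2.1, Appendix 5), abnormal pregnancy outcomes count as SAEs (9.2.6), and a pregnancy test is scheduled at the Final Visit. For completers the nominal shortfall is about a week at most, and usually nothing. On this view, extending collection is a preference and corrects no error. Much of that stands for completers. It does not answer the withdrawal case: the later rules are passive and limited to related SAEs, and a test at the termination visit cannot detect a conception that comes after it.

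Four stronger readings are tempting, and the documents do not support them.

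- **That partner pregnancies fall in the same gap.** The 3-month period is set for women. Male subjects are bound only during the study, so collecting partner pregnancies up to the Final Visit matches their obligation.
- **That pregnancies are reported late.** For a female subject Appendix 5 requires 24 hours, and 9.2.6 says nothing different. For partners, the 24 hours in 9.2.6 can be read as first notice and the 2 weeks in Appendix 5 as the deadline for the consented form, so a site could meet both. What remains is that the text does not say so, and the cross-reference that might settle it is blank.
- **That the protocol defines a 3-month risk or exposure window.** It sets a contraception period. Table 11 mentions a period of risk from the product but gives it no length.
- **That a completer may be seen only 76 days after the last dose.** Pairing the latest Week 36 dose (252 + 4 = 256) with the earliest Final Visit (336 − 4 = 332) gives 76 days. But when V5 doubles as the Final Visit, its own window of 12 weeks ±4 days sets a minimum of 80.

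**Conclusion.** The point holds for female subjects. Their contraception period and the collection of their pregnancies end at different times, and the difference is material for women withdrawn soon after an injection: about 11 of 13 weeks in the 2-week example. For completers it is nominally 5 to 8 days, only when the last dose is at Week 36, and a Week 36 dose given early can remove it.

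This rests on taking 3 months as 89 to 92 days and on reading participation as ending at the Final or termination visit. That few pregnancies would be missed is a judgement, since the documents give no rate and no count of women of childbearing potential. The issue is minor: it concerns the completeness of one part of the safety record and touches no efficacy result. The wording faults in 9.2.6 are real but editorial, and they do not show that any report would be late.

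**What to change.** Reconcile criterion 10b ii in 6.1.1, section 9.2.6 and Appendix 5 so that collection for female subjects, including those withdrawn, runs to the end of whatever contraception period the protocol keeps, counted from the last dose. The length of that period is for the sponsor to settle; the point here is only that the two ends should agree.

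In the same amendment:

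- name female subjects in the collection rule of 9.2.6;
- replace the placeholder [X] with the actual appendix number;
- state how the 24-hour notice in 9.2.6 and the 2-week rule for partner pregnancies in Appendix 5 relate, for example as notice followed by the consented form, if that is what was meant.

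The cost is amendment wording and one contact with each woman of childbearing potential whose Final or termination visit falls before her contraception period ends.

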12.6. APPENDIX 6: Liver Safety Required Actions and Follow up Assessments

In order to secure the subject's safety and evaluate the causes of liver event, **the criteria for discontinuation and follow-up based on the liver function test values in the phase III-IV studies** will be stipulated.

Criteria for discontinuation based on the liver function test values in the phase III-IV studies and necessary follow-up

Criteria for discontinuation based on the liver function test values	
ALT	ALT \geq 8xULN
ALT increase	ALT \geq 5xULN but <8xULN persists for \geq 2 weeks ALT \geq 3xULN but <5xULN persists for \geq 4 weeks
Bilirubin ^{1,2}	ALT \geq 3xULN and bilirubin \geq 2xULN (>35% direct bilirubin)
INR ²	ALT \geq 3xULN and INR>1.5, if INR measured
Cannot Monitor	ALT \geq 5xULN but <8xULN and cannot be monitored weekly for \geq 2 weeks ALT \geq 3xULN but <5xULN and cannot be monitored weekly for \geq 4 weeks
Symptom ³	ALT \geq 3xULN associated with symptoms (new or worsening) believed to be related to liver injury or hypersensitivity
Necessary measures and assessment items for liver event	
Actions	Follow Up Assessments

 Immediately discontinue the administration of the investigational product. Report it to GSK within 24 hours. Complete the liver event CRF and complete an SAE data collection tool if the event also meets the criteria for an SAE². Perform liver event follow up assessments Monitor the participant until liver chemistries resolve, stabilize, or return to within baseline (see MONITORING below) Do not restart/rechallenge participant with study treatment unless allowed per protocol and GSK Medical Governance approval is granted If the resumption/re-administration of the investigational product is not stipulated in the protocol or approved by GSK's Medical Governance, the administration of the investigational product will be discontinued 	
 Viral hepatitis serology⁴ Obtain INR and recheck with each liver chemistry assessment until the transaminases values show downward trend Only in those with underlying chronic Hepatitis B at study entry (identified by positive Hepatitis B surface antigen) quantitative Hepatitis B DNA and Hepatitis delta antibody⁵ Serum creatine phosphokinase (CPK) and lactate dehydrogenase (LDH). Fractionate bilirubin, if total bilirubin \geq 2xULN Obtain complete blood count with differential to assess eosinophilia Record the appearance or worsening of clinical symptoms of liver injury, or hypersensitivity, on the AE report form Record use of concomitant medications on the concomitant medications report form including acetaminophen, herbal remedies, other over the counter medications.


permanently and the follow-up prescribed in the protocol 8.1. will be conducted.
 
MONITORING:
 
For bilirubin or INR criteria:
 
 • Repeat liver chemistries (include ALT, AST, alkaline phosphatase, bilirubin) and perform liver event follow up assessments within 24 hrs • Monitor participants twice weekly until liver chemistries resolve, stabilize or return to within baseline • A specialist or hepatology consultation is recommended 
For other criteria:
 
 • Repeat liver chemistries (include ALT, AST, alkaline phosphatase, bilirubin) and perform liver event follow up assessments within 24-72 hrs • Monitor participants weekly until liver chemistries resolve, stabilize or return to within baseline 	
 • Record alcohol use on the liver event alcohol intake case report form (CRF) page 
For bilirubin or INR criteria:
 
 • Anti-nuclear antibody, anti-smooth muscle antibody, Type 1 anti-liver kidney microsomal antibodies, and quantitative total immunoglobulin G (IgG) or gamma globulins. • Liver imaging (ultrasound, magnetic resonance, or computerised tomography) and /or liver biopsy to evaluate liver disease; complete Liver Imaging and/or Liver Biopsy CRF forms.
--	--

1. Serum bilirubin fractionation should be performed if testing is available. If serum bilirubin fractionation is not immediately available, discontinue study treatment for that participant if ALT $\geq 3xULN$ and bilirubin $\geq 2xULN$. Additionally, if serum bilirubin fractionation testing is unavailable, record presence of detectable urinary bilirubin on dipstick, indicating direct bilirubin elevations and suggesting liver injury.

All events of ALT $\geq 3xULN$ and bilirubin $\geq 2xULN$ (>35% direct bilirubin) or ALT $\geq 3xULN$ and INR>1.5, if INR measured which may indicate severe liver injury (possible 'Hy's Law'), must be reported as an SAE (excluding studies of hepatic impairment or cirrhosis); INR measurement is not required and the threshold value stated will not apply to participants receiving anticoagulants New or worsening symptoms believed to be related to liver injury (such as fatigue, nausea, vomiting, right upper quadrant pain or tenderness, or jaundice) or believed to be related to hypersensitivity (such as fever, rash or eosinophilia)

Includes: Hepatitis A IgM antibody; Hepatitis B surface antigen (HbsAg) and Hepatitis B Core Antibody (IgM); Hepatitis C RNA; Cytomegalovirus IgM antibody; Epstein-Barr viral capsid antigen IgM antibody (or if unavailable, obtain heterophile antibody or monospot testing); Hepatitis E IgM antibody

Criteria for follow-up with continued treatment based on the liver function test values in the phase III-IV studies

Criteria for follow-up based on liver test function values – Liver events to be followed	
Criteria	Actions

ALT \geq5xULN and <8xULN and bilirubin <2xULN without symptoms believed to be related to liver injury or hypersensitivity, and who can be monitored weekly for 2 weeks.
 
OR
 
ALT \geq3xULN and <5xULN and bilirubin <2xULN without symptoms believed to be related to liver injury or hypersensitivity, and who can be monitored weekly for 4 weeks.
	
 • Notify the GSK medical monitor within 24 hours of learning of the abnormality to discuss participant safety. • Participant can continue study treatment • Participant must return weekly for repeat liver chemistries (ALT, AST, alkaline phosphatase, bilirubin) until they resolve, stabilise or return to within baseline • If at any time participant meets the liver chemistry stopping criteria, proceed as described above • If ALT decreases from ALT \geq5xULN and <8xULN to \geq3xULN but <5xULN, continue to monitor liver chemistries weekly. • If, after 4 weeks of monitoring, ALT <3xULN and bilirubin <2xULN, monitor participants twice monthly until liver chemistries normalize or return to within baseline.

